19.3 Appendix 3 – Subject Diary and Memory Aid Sample Pages

	SUBJECT DIARY
Study Name	A Randomized, Observer-blind, Active Comparator-controlled, Multicenter, Phase 3 Study to Assess the Efficacy, Safety, and Immunogenicity of a Plant-derived Quadrivalent VLP Influenza Vaccine in Adults 65 Years of Age and Older
Protocol Number	CP-PRO-QVLP-014
Sponsor	Medicago R&D Inc. [name]
Clinical site Address	[name]
Principal Investigator Name	NLY. DU
Clinical Research Coordinator	SAMPLE ONLY. DO IS
24-hour Emergency Number	SAM

INSTRUCTIONS

The diary is to help you keep track of information needed during this study.

You will need to refer to this diary during the telephone contacts. Any greyed out sections are to be left blank and will be completed by the site personnel.

To complete this document, use ink. No pencil or liquid paper is allowed. If you made a mistake, cross out the incorrect information, initial and date, and write the correct answer beside it.

The date should be recorded with 2 digits for day, 3 letters for month and 4 digits for year:

January	JAN	April	APR	July	JUL	October	OCT
February	FEB	May	MAY	August	AUG	November	NOV
March	MAR	June	JUN	September	SEP	December	DEC

From vaccination:

- To Day 7:
- Reactions (temperature, swelling, redness, and pain at injection site, headache, fatigue, muscle aches, joint aches, chills, general discomfort/uneasiness, swelling in the axilla and the neck) should be recorded at approximately the same time each evening.
 - Fill in the table for the first 7 days after you receive your vaccine dose; for each day, enter the WORST grade for each symptom for that day;
 - For temperature, use the thermometer you were given at the clinic. Do not eat or drink prior to taking your temperature. Take your temperature at approximately the same time each evening and at any other time you feel feverish. Record the highest temperature of each day.
- To Day 21:
- Side effects (symptoms) should all be recorded. You do NOT need to collect reactions that you reported as Day 0 to Day 7 reactions (listed in the previous point).
- All medication should also be recorded. Examples may include prescription drugs (including vaccines), over-the-counter drugs helbal supplements and/or vitamins. Indicate each intake of medication you are usually taking as needed.

From Day 14:

- Record below respiratory illness and influenza-like Illness symptoms.
- Any medication taken for respiratory illness and influenza-like illness symptoms should also be recorded.

NOTE: Each medication must be associated to a problem, but each problem does not require a medication associated with it.

Day 7	Day 14	Day 21				
dd mmm yyyy	dd mmm yyyy	dd mmm yyyy				

Medicago R&D Inc. Page 84 of 90

	REACTIONS (DAY 0 to DAY 7)											
Day 0 to Day 7		30 min, Post-dose	Evening, day of dose	1 st Day after dose	2 nd Day after dose	3 rd Day after dose	4 th Day after dose	5 th Day after dose	6 th Day after dose	7 th Day after dose		
Date (dd-mmm-yyyy)												
Oral Tamparatura	°C											
Oral Temperature	Causality					45	ê					
Redness where the injection was given	Grade					40'T						
	Use the measuring tool given to you at the site to estimate the size of the red area around the injection site and indicate the grade above.											
Swelling where the	Grade			E ON	>							
injection was given	Use the measuring tool given to you at the see to estimate the size of the swollen area around the injection site and indicate the grade above.											
Pain at vaccine	Grade		SAL									
injection site	0= No symptom; 1= Mild: Does not interfere with activity; 2= Moderate: Repeated use of non-narcotic pain reliever >24 hours or interferes with activity; 3= Severe: Any use of narcotic pain reliever or prevents daily activity; 4= Potentially life-threatening: Visit to Emergency room or hospitalization.											
MD initials and date:	-	L	dd mmm		j		•		-			
Comments: □ N/AP	-											

	REACTIONS (DAY 0 to DAY 7)											
Day 0 to Day 7		30 min, Post-dose	Evening, day of dose	1 st Day after dose	2 nd Day after dose	3 rd Day after dose	4 th Day after dose	5 th Day after dose	6 th Day after dose	7 th Day after dose		
Headache	Grade											
пеадаспе	Causality					ر د	Ê					
Muscle aches	Grade					30TO						
	Causality				A.DO	,						
Joint aches	Grade			TO N	D.							
Joint aches	Causality		SAM	PLE								
Fatigue	Grade		SAR									
Taligue	Causality											
	mptom; 1= Milo e: Any use of na											
MD initials and date:		L	dd mmm	уууу	j							
Comments: □ N/AP	-											

Medicago R&D Inc.

Page 86 of 90

REACTIONS (DAY 0 to DAY 7)											
Day 0 to Day 7		30 min, Post-dose	Evening, day of dose	1 st Day after dose	2 nd Day after dose	3 rd Day after dose	4 th Day after dose	5 th Day after dose	6 th Day after dose	7 th Day after dose	
C1 :11	Grade										
Chills	Causality					æ					
Feelings of general discomfort or uneasiness	Grade				46	TUSE					
	Causality				100 K						
Feeling of swelling in the neck	Grade			WI	. *						
	Causality		SAMPI	E							
Feeling of swelling	Grade		SAME								
in the axilla	Causality										
	nptom; 1= Milde: Any use of na										
MD initials and date:		L	dd mmm	уууу	j						
Comments: ☐ N/AP											

S	IDE EI	FFECTS (S	YMPT	OMS)		
Cil Effects (see a constant)	Grade	START		STOP		Did you receive
Side Effects (symptoms)	(See below)	Date	Time	Date	Time	medical care?
						□ Yes □ No
						□ Yes □ No
		ONLY. T	~10	TUSE		□ Yes □ No
		T.Y.IV	9			□ Yes □ No
	MPL	Ó				□ Yes □ No
À						□ Yes □ No
						□ Yes □ No
						□ Yes □ No
						□ Yes □ No
						□ Yes □ No

GRADES 1= Does not interfere with activity; 2= Some interference with activity not requiring medical intervention; 3= Prevents daily activity and requires medical intervention; 4= Visit to Emergency room or hospitalization.

	MEDICATION												
(Name, D	Medicat lose, Route		ency)	S	Start date	Stop	date	Reason(s) w are takin medicati	g this				
							SE						
					MLY. D	ONOT	O'Y						
			مر ا	Ê	MIY.								
		SA	Mir										
	Dose				Route			Frequency					
Capsule	Tablespoon	g	Oral		Intramuscular	Ophthalmic	Once a day	Every other day					
Tablet	Teaspoon	mcg	Topical		Nasal	Intra-articular Rectal	Twice a day	Every 3 days	Intermittent				
Ring Application	Puff Drops	mg IU	Inhalati Intraute		Intravenous Transdermal	Sublingual	3 times/day 1x per week	Every 2 weeks Every 6 months	Once As needed				
Lozenge	mL	Units	Vaginal		Subcutaneous	Unknown	2x per week	Every hour	Unknown				
Syringe	%	Unknown					Once a month	Once a year					

Confidential Information

Medicago R&D Inc. Page 89 of 90

RESPIRATORY ILLNESS & INFLUENZA-LIKE ILLNESS SYMPTOMS

From Day 14 to the end of the study, record your symptoms when you experience one of the following. Use a checkmark (" $\sqrt{}$ ") for each symptom you do have.

If you have a checkmark for any of the seven symptoms shaded in grey, call the site as soon as possible.

STAR' Date	Г Time	Sneezing	Stuffy / Runny Nose	Sore Throat	Cough	Sputum	Wheezing	Difficulty Breathing	Chills	Tiredness	Headache	Muscle Aches	Fever*	List if one of the following: feeling feverish, nausea, vomiting, or diarrhea
											À.			
										US				
									120					
							W	X.V						
						OLE	, O							
					S	Mr.								

* Fever: indicate a checkmark if your oral temperature is > 99 °F or > 37.2 °C

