10.3.1.1 Solicited Local and Systemic Reactions

Subjects will be monitored for both solicited local reactions (erythema, swelling, and pain at the injection site) and solicited systemic reactions (fever, headache, fatigue, muscle aches, joint aches, chills, a feeling of general discomfort, swelling in the axilla, and swelling in the neck) from the time of vaccination through Day 7. While the subjects remain in the clinic following vaccine administration, staff will monitor them for local and systemic reactions; after release from the clinic facility, from the evening of Day 0 to the evening of Day 7, subjects will measure and record their local and systemic reactions in their diary.

The intensity of the solicited local and systemic reactions will be graded as: mild (1), moderate (2), severe (3), or potentially life threatening (4) (please refer to Table 6). Their causal relationship with the study vaccine will be assessed by the Investigator (definitely not related, probably not related, possibly related, probably related or definitely related); see Section 13.1.9 for the definition of the causal relationships.

Medicago R&D Inc. Page 54 of 90

Table 6 Severity Grades for Solicited Local and Systemic Reactions

Symptoms	Severity						
	None	Grade 1 (Mild)	Grade 2 (Moderate)	Grade 3 (Severe)	Grade 4 (Potentially life- threatening)		
Injection Site Reactio	ns (Local Rea	ctions)		1	•		
Erythema (redness)	< 25 mm	25 - 50 mm	51 - 100 mm	> 100 mm	Necrosis or exfoliative dermatitis		
Swelling	< 25 mm	25 - 50 mm and does not interfere with activity	51 – 100 mm or interferes with activity	> 100 mm or prevents daily activity	Necrosis		
Pain	None	Does not interfere with activity	Repeated use of non-narcotic pain reliever for more than 24 hours or interferes with activity	Any use of narcotic pain reliever or prevents daily activity	Results in a visit to emergency room (ER) or hospitalization		
Solicited Systemic Res	actions						
Fever (°C or °F)	< 38.0 °C < 100.4 °F	38.0 - 38.4 °C 100.4 - 101.1 °F	38.5 - 38.9 °C 101.2 - 102.0 °F	39.0 - 40.0 °C 102.1 - 104.0 °F	> 40.0 °C > 104.0 °F		
Headache	None	No interference with activity	Repeated use of non-narcotic pain reliever for more than 24 hours or some interference with activity	Significant; any use of narcotic pain reliever or prevents daily activity	Results in a visit to emergency room (ER) or hospitalization		

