10.3.2 Safety Endpoints

10.3.2.1 Secondary Endpoints

- Percentage, intensity, and relationship to vaccination of immediate complaints (15 minutes post-vaccination);
- Percentage, intensity, and relationship to vaccination of solicited local and systemic signs and symptoms (for seven days following study vaccine administration);
- Percentage, intensity, and relationship of TEAEs for 21 days following study vaccine administration;
- Occurrences of deaths, SAEs, AEs leading to withdrawal, and NOCDs up to the end of the surveillance period.

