17.3.1 Diary and Memory Aid

Subjects will be provided with a diary in which to record reactions and other safety information. Subject diaries are considered source documents; the diary will be returned by the subject to the site after Day 21 (the method of return will be defined in the study-specific documentation) and kept with each subject's study chart. In the event the diary is lost by the subject, information collected by the coordinator or designee and information recalled by the subject will serve as the source data for this subject. The recalled information will be captured in the source documents.

Corrections to data entered by the subject in the diary should only be performed by the subject him/herself, when possible. Clarifications can be made in the comment section of the diary by the study personnel if the subject is not present onsite to make the correction him/herself.

Subjects will be provided with a memory aid to record information on respiratory illnesses and ILIs, and to record information on SAEs, NOCDs, AEs leading to withdrawal, and reportable concomitant medications from the Day 21 visit to the end of the study. These memory aids will not be collected by the site and are intended to be used by the subject to help them in reporting this information to site staff.

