19.1 Appendix 1 – Sample Ruler to Measure Local Reactions

Site Reaction Measuring Ruler

Grading	Grading for erythema and swelling where the vaccine was given							
Grade 0	None or less than 25 mm							
Grade 1	Between 25 mm and 50 mm							
Grade 2	Between 51 and 100 mm							
Grade 3	More than 100 mm							
Grade 4	Skin/tissue loss at the injection site (blister or ulcer formation) of any size							

Medicago R&D Inc. Page 80 of 90

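### Used as printed, the sample ruler and diary grade injection-site swelling on size alone, so some activity-limiting swelling of 25–100 mm is recorded one or two grades below Table 6

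*Protocol*

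**What the plan says.** Protocol 10.1.2.3 tells subjects how to measure redness and swelling diameter with a template, describes that template as measuring in mm, and says the severity of local reactions is graded by the FDA 2007 scale as set out in Table 6. Table 6 (Protocol 10.3.1.1; the same content is SAP Table 4 in SAP 10.1) has separate rows for erythema and swelling. Erythema is graded on size up to Grade 3. Swelling has a second criterion:

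- Grade 1: "25 - 50 mm and does not interfere with activity"
- Grade 2: "51 – 100 mm or interferes with activity"
- Grade 3: "> 100 mm or prevents daily activity"

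The sample ruler in Protocol 19.1 merges the two reactions under one heading, "Grading for erythema and swelling where the vaccine was given", and sets Grades 0 to 3 by millimetres only. In the sample diary (Protocol 19.3) the swelling row has a Grade field and the instruction to "estimate the size of the swollen area around the injection site and indicate the grade above". It has no field for the diameter and no wording on activity. The pain row below it does print the activity wording for each grade.

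Protocol 17.3.1 states: "Subject diaries are considered source documents". The introduction to Protocol Section 19 says the appendix documents are examples and that those used in the trial may differ slightly.

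**The concern.** The named scale and the tools that would produce the recorded grade apply different rules to the same reaction. For swelling, Table 6 joins size and activity with an or at Grades 2 and 3, while the tools keep only the size half. A subject who follows the diary instruction exactly can therefore enter a grade that Table 6 would not give.

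Two uses of the grade are exposed. First, the intensity of solicited reactions is a secondary safety endpoint (Protocol 10.3.2.1), and SAP 10.3 tabulates each individual reaction by maximum severity and summarises severe and potentially life-threatening solicited reactions. Second, the grade drives conduct. Subjects are told to contact the site for solicited reactions above Grade 2 (Protocol 10.1.2.3), and the Investigator is to be informed of these within 48 hours of the site becoming aware (Protocol 10.1.3). A Table 6 Grade 3 swelling entered as Grade 1 or 2 does not meet that threshold.

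**Working it through.** No sample size, power or event count bears on this point, and the plan states no figure to reproduce. The check applies both grading rules to every combination of the four size bands and three activity levels that Table 6 uses: 4 × 3 = 12 combinations.

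Inputs: the Table 6 swelling row (Protocol 10.3.1.1), the ruler bands (Protocol 19.1) and the diary swelling instruction (Protocol 19.3). Grade 4 is left out because neither source sets it by size or activity.

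| Swelling size | Effect on activity | Ruler and diary | Table 6 | Result |
|---|---|---|---|---|
| < 25 mm | none | 0 | 0 | agree |
| < 25 mm | interferes | 0 | 0 by size, 2 by activity | ambiguous |
| < 25 mm | prevents | 0 | 0 by size, 3 by activity | ambiguous |
| 25–50 mm | none | 1 | 1 | agree |
| 25–50 mm | interferes | 1 | 2 | one grade low |
| 25–50 mm | prevents | 1 | 3 | two grades low |
| 51–100 mm | none | 2 | 2 | agree |
| 51–100 mm | interferes | 2 | 2 | agree |
| 51–100 mm | prevents | 2 | 3 | one grade low |
| > 100 mm | none | 3 | 3 | agree |
| > 100 mm | interferes | 3 | 3 | agree |
| > 100 mm | prevents | 3 | 3 | agree |

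Counts: agree 1 + 1 + 2 + 3 = 7; disagree 2 + 1 = 3; ambiguous 2; total 12. All three disagreements are under-grades by the tools. Two of them (25–50 mm and 51–100 mm, each preventing daily activity) move a Table 6 Grade 3 to Grade 2 or below, out of the severe category and under the contact threshold.

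The two ambiguous cells arise inside Table 6: the None column applies to anything under 25 mm, while the or clauses at Grades 2 and 3 carry no minimum size. The tools cannot be called wrong there.

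The recorded grade does not allow a later correction by itself. A recorded Grade 1 covers Table 6 Grades 1, 2 and 3, and a recorded Grade 2 covers Table 6 Grades 2 and 3. Without an activity entry these cannot be separated.

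**The case against.** The strongest reply is that the appendix pages are samples. They are marked as such, the protocol says the final forms may differ slightly, and the diary, eCRF and completion guidelines actually used are not in the file. The body text governs, and it already requires measurement in mm and grading by Table 6. This stands in part: nobody can say from these documents that wrong grades will enter the data, only that they would if the forms are used as shown. It does not remove the point. Adding an activity criterion changes the grading rule, so it is more than a slight difference, and no section commits to capturing activity for swelling or to regrading it.

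A reader might go further in four ways that the documents do not support.

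- **The information is lost for good.** The diary has a comments line and a place for physician initials, Protocol 17.3.1 lets staff add clarifications, and the Day 1 and Day 8 calls ask about changes in health. An ad hoc note is possible. What is missing is systematic capture.
- **The headline severe row is wrong for all these subjects.** That row counts any severe solicited reaction. Pain is graded on activity on the same diary page, so a subject whose small swelling is disabling because it hurts may still be counted. The swelling-specific rows are the ones exposed.
- **The diary's 30-minute column conflicts with the 15-minute endpoint.** Protocol 10.1.2.3 sets observation at a minimum of 15 minutes and allows a further 15 minutes, which reaches 30. The column label is compatible with that window.
- **The ruler's Grade 4 inflates severity.** Its text is "Skin/tissue loss at the injection site (blister or ulcer formation) of any size". This can be read as a lay rendering of the necrosis and exfoliative dermatitis in Table 6. It calls for a consistency check and does not show an error.

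**Conclusion.** The point holds for Grades 0 to 3 of swelling. If the sample ruler and diary are used as shown, three of the 12 size-by-activity combinations are under-graded: 25–50 mm interfering with activity (1 instead of 2), 25–50 mm preventing daily activity (1 instead of 3) and 51–100 mm preventing daily activity (2 instead of 3). Below 25 mm no conclusion is possible until Table 6 is clarified.

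The consequence is limited to swelling-specific severity summaries, which can be understated in both arms, and to a possible miss of the above-Grade-2 contact trigger. The documents give no frequency of activity-limiting swelling in either arm, so neither the number of subjects affected nor any effect on the comparison between arms can be computed. Safety is summarised descriptively, and the efficacy analyses are untouched. The conclusion assumes that the final forms keep the size-only rule and that sites do not regrade on their own initiative.

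**What to change.** Reconcile the ruler and diary with Table 6 before first vaccination. In the diary's swelling row, record the diameter in mm and add one activity item with three options (does not interfere, interferes, prevents daily activity). Derive the swelling grade from these two entries by Table 6, and say so in SAP 10.3. State in Table 6 and SAP Table 4 how swelling under 25 mm that affects activity is to be classified. Check the ruler's Grade 4 wording against Table 6 at the same time.

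The cost is a revised diary page and ruler, and one extra item per evening from Day 0 to Day 7, which is 8 entries per subject (7 − 0 + 1). No visit or procedure is added. Because the contact trigger depends on the grade, the site needs the derived grade, or the two entries behind it, at the Day 1 and Day 8 calls as well as at analysis.

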		14.2.1. General	51
	14.3.	Headers	51
		14.3.1. Display Titles	52
		14.3.2. Column Headers	52
		14.3.3. Body of the Data Display	52
15.	QUA	LITY CONTROL	55
16.	APPE	ENDICES	56
LIS	T OF 1	ΓΑΒLΕ	
Tab	le 1 Tin	me and Events Schedule: General Information	19
Tab	le 2 Tin	me and Events Schedule: Respiratory Illness Onset	21
Tab	le 3 Est	timated Blood Volume Drawn	22
LIS	T OF F	FIGURE	
Figu	ire 1 Flo	owchart of Study Procedures	13
Figu	ire 2 Flo	owchart of Process of Respiratory Illness Report	14

GLOSSARY OF ABBREVIATIONS

AE	Adverse Event
ANCOVA	Analysis of Covariance
ANOVA	Analysis of Variance
ARV _C	Attack Rate in Subjects Vaccinated with the Active Comparator
ARV_V	Attack Rate in Subjects Vaccinated with the Quadrivalent VLP
ATC	Anatomical Therapeutic Chemical
BMI	Body Mass Index
BP	Blood Pressure
CI	Confidence Interval
CMI	Cell-Mediated Immune (response)
eCRF	Electronic Case Report Form
EMA	European Medicines Agency
FAS	Full Analysis Set
FDA	Food and Drug Administration
GMA	Geometric Mean Area
GMT	Geometric Mean Titer
GMFR	Geometric Mean Folder Rise
ICF	Informed Consent Form
ICH	International Conference on Harmonization
ILI	Influenza-like Illness
IM	Intramuscular
IPP	Immunogenicity Per Protocol
НІ	Hemagglutination Inhibition
HIV	Human Immunodeficiency Virus
HR	Heart Rate
LL	Lower limit

MedDRA	Medical Dictionary for Regulatory Activities
Min	Minimum
MN	Microneutralization
NOCD	New Onset of Chronic Disease
NP	Nasopharyngeal
N/A	Not Applicable
ОТ	Oral Temperature
PBMC	Peripheral Blood Mononuclear Cell
PP	Per Protocol
PT	Preferred Term
RT-PCR	Reverse Transcription Polymerase Chain Reaction
SAE	Serious Adverse Event
SAP	Statistical Analysis Plan
SAS	Safety Analysis Set
SAS®	Statistical Analysis System®
SC	Seroconversion
SD	Standard Deviation
SMQ	Standardized MedDRA Query
SOC	System Organ Class
SOP	Standard Operating Procedure
SRH	Single Radial Hemolysis
TEAE	Treatment Emergent Adverse Event
TLF	Table, Listing and Figure
VE	Vaccine Efficacy
VLP	Virus-like Particle
WHO	World Health Organization
UL	Upper limit

2. PURPOSE

The purpose of this statistical analysis plan (SAP) is to ensure that the data listings, summary tables and figures that will be produced and the statistical methodologies that will be used are complete and appropriate to allow valid conclusions regarding the study objectives described under Medicago Protocol CP-PRO-QVLP-014 titled "A Randomized, Observer-blind, Active Comparator-controlled, Multicenter, Phase 3 Study to Assess the Efficacy, Safety, and Immunogenicity of a Plant-derived Quadrivalent VLP Influenza Vaccine in Adults 65 Years of Age and Older" Final Protocol version 1.2 dated 24July2018.

2.1. Responsibilities

will perform the statistical analyses and is responsible for the production and quality control of all tables, listings and figures (TLFs).

Medicago will perform review of all tables, figures and listings before the finalization.

2.2. Timings of Analyses

The primary analysis is planned after all subjects complete the final study visit or terminate early from the study, and database is cleaned and locked.

3. STUDY OBJECTIVES

3.1. Primary Objective

To evaluate the efficacy, relative to an active comparator, of a single 30 μg/strain dose
of the Quadrivalent Virus-like Article (VLP) Influenza Vaccine, against protocoldefined influenza-like illness (ILI) caused by any influenza viral type/subtype (RTPCR);

3.2. Secondary Objectives

Efficacy:

- To evaluate the efficacy, relative to an active comparator, of a single 30 μg/strain dose
 of the Quadrivalent VLP Influenza Vaccine, against laboratory-confirmed protocoldefined influenza-like illness (ILI) caused by vaccine-matched strains (sequential RTPCR & serotyping);
- To evaluate the efficacy, relative to an active comparator, of a single 30 μg/strain dose
 of the Quadrivalent VLP Influenza Vaccine, against laboratory-confirmed protocoldefined respiratory illness caused by vaccine-matched strains (sequential RT-PCR &
 serotyping);
- 3. To evaluate the efficacy, relative to an active comparator, of a single 30 μg/strain dose of the Quadrivalent VLP Influenza Vaccine, against laboratory-confirmed protocoldefined respiratory illness caused by any influenza viral types/subtypes (matched, mismatched, and un-typed) (sequential RT-PCR);
- 4. To evaluate the efficacy, relative to an active comparator, of a single 30 μ g/strain dose of the Quadrivalent VLP Influenza Vaccine, as measured by the incidence of subjects presenting with symptoms of protocol-defined ILI, regardless of laboratory results.
- 5. To evaluate the efficacy, relative to an active comparator, of a single 30 μg/strain dose of the Quadrivalent VLP Influenza Vaccine, against laboratory-confirmed protocoldefined influenza-like illness (ILI) caused by any influenza viral types/subtypes (matched, mismatched, and un-typed) (sequential RT-PCR) according to prior exposure to influenza vaccines;

Safety:

1. To assess the safety and tolerability, relative to an active comparator, of a single $30 \mu g/strain$ dose of the Quadrivalent VLP Influenza Vaccine.

Immunogenicity:

 To assess, in a subset of 420 subjects (210 subjects per treatment group), the immunogenicity of a single 30 μg/strain dose of Quadrivalent VLP Influenza Vaccine and an active comparator, as measured by Hemagglutination Inhibition (HI) assay, Microneutralization (MN) assay, and Single Radial Hemolysis (SRH) assay against homologous and heterologous (HI only) influenza strains.

